## 5. Inclusion/Exclusion Criteria

We will recruit healthy volunteers who may have consumed prescription opioids in the past either recreationally or for medical purposes, but are not currently dependent (Table 1). Restricting our sample to completely opiate naïve individuals would not be feasible, because verifying a history of no opiate use may not be possible, and because we did not want to exclude participants who received clinically-indicated prescriptions. Non-dependent drug using participants have been strategically chosen to minimize potential confounds with current opioid dependence (e.g., tolerance, presence of pain) and human subject concerns regarding need for treatment. Use of non-dependent participants is a common practice in laboratory studies of drug effects and there is no evidence to suggest this exposure puts individuals at risk for developing drug dependence (see Human Subjects section). Finally, females will be enrolled in the study during the 1st two weeks of their menstrual cycle (confirmed via diary and progesterone) to control for hormonal influence on opioid effects and pain. We will not exclude females taking birth control but may include birth control as a covariate in the statistical analyses.

Table 1. Study Eligibility Criteria	
Inclusion	Exclusion
1. Provide a urine sample that tests negative for opioids, methadone, buprenorphine, oxycodone, amphetamine, cocaine, and benzodiazepines	1. Answer “yes” to question 1 of the Brief Pain Inventory (89) to assess the presence of chronic pain.
2. Negative ethanol breath test (0.000)	2. Current use of opioids or other medications for pain
3. Aged 21-50	3. Meet DSM-5 criteria for current or lifetime alcohol or drug use disorder (excluding nicotine)
4. Deemed medically eligible to take hydromorphone	4. Self-report any illicit drug use in the past 7 days
	5. Self-report opioid use $\geq$ 5 days in the past 30
	6. Evidence of opioid physical dependence at screening or following 1 st night in CRU (following confirmed opioid abstinence)
	7. Allergy to hydromorphone or other opioid agonists
	8. Experience an adverse event that warrants opioid antagonist treatment following 1 st hydromorphone dose.
	9. If female, not be pregnant or breastfeeding
	10. Presence of any clinically significant medical (e.g., chronic renal insufficiency, history of myocardial infarction, seizure disorder) and/or psychiatric illness (e.g., schizophrenia, bipolar disorder) that may interfere with study participation.
	11. BMI >30 (obese category)

## 6. Drugs/ Substances/ Devices

- a. The rationale for choosing the drug and dose or for choosing the device to be used.

We will administer oral hydromorphone in this study. We have selected hydromorphone because it is a prototypic, selective, potent, full MOR agonist that is frequently used in abuse liability studies as a surrogate for heroin, it is not subject to P450 metabolism, it has good oral bioavailability, there are no apparent sex effects of metabolism, it is used clinically for the treatment of pain, there is a wealth of literature available to which our research findings can be compared and interpreted, and we have several years experience administering it under double-blind, laboratory conditions (4, 7, 8, 128-135). The doses of hydromorphone chosen for this study are supported by a study conducted by Walsh et al., (2008), in which oral hydromorphone was administered to non-dependent individuals in doses up to 25mg (136). The authors of that study had no instances of respiratory depression or reductions in SpO2 at any of the doses administered. That study compared the reinforcing effects of oral hydromorphone with the two prominently abused opioid agonists hydrocodone and oxycodone within healthy volunteers who had a history of recreational opioid use but were not opioid dependent. Prior to beginning the study, the researchers conducted a pilot study wherein 5 doses of oral hydromorphone [2.5 mg – 35mg] were administered to enable identification of several safe, tolerable and detectable doses for study administration. The researchers reported the 2 lowest doses [2 and 5mg] were inactive within a population of recreational but non-dependent individuals, and ultimately selected three mid-range doses [10mg, 17.5mg, 25mg] based upon evidence of safety and tolerability.

We have chosen to deliver doses lower than those administered by that study so we may evaluate whether there are individual differences in the ability to detect the low dose of hydromorphone. Participants in our study will receive three active hydromorphone doses. The first dose participants will receive is the mid-level dose, which will be administered on study Day 2. Any participant who has a negative reaction to this dose will be discharged from the study. The participants will receive placebo, low, and high doses on Days 3-5 of the study; the order of doses will be randomized and counter-balanced. These doses were deemed safe in the same participant population in the Walsh study, they produced a documented detectable range of subjective effects, and they represent suprathreshold doses consistent with those abused recreationally. Ultimately, we feel confident these dose values do not impose any unique risk above and beyond that presented by the administration of hydromorphone.

Generic powdered hydromorphone will be encapsulated using size 0, opaque, hard gelatin capsules; placebo will be size and weight matched and will contain microcrystalline cellulose filler. A pharmacy member with no participant interaction will conduct the dose randomization. All medication administration will be supervised and a medical staff member will be available to address any adverse events or to break the medication blind.

- b. Justification and safety information if FDA approved drugs will be administered for non-FDA approved indications or if doses or routes of administration or participant populations are changed.

Hydromorphone hydrochloride is a pure mu opioid agonist that can be administered in oral, rectal, intramuscular (IM), or intravenous (IV) formulations for the indication of acute and/or chronic pain. We have chosen to administer hydromorphone orally in this study to reduce the potential for side effects and adverse events associated with the more direct parenteral administration, and to increase the clinical relevance of the study by administering the most commonly-abused formulation of hydromorphone. This will also extend the time course of hydromorphone effects, which will help us to achieve our study aims. When administered orally, hydromorphone is rapidly absorbed through the gastrointestinal tract and subjected to extensive first-pass metabolism. Exposure to hydromorphone is proportional to the dose range, with *in vivo* bioavailability of an 8mg tablet being approximately 24%. Following oral administration, peak plasma level of hydromorphone is generally attained in 30 – 60 minutes, and approximately 95% of hydromorphone is metabolized to hydromorphone-3-glucuronide via glucuronidation in the liver. There is no apparent effect of sex on the pharmacokinetics of hydromorphone.

- c. Justification and safety information if non-FDA approved drugs without an IND will be administered.

N/A

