#### 1. Abstract

- a. Provide no more than a one page research abstract briefly stating the problem, the research hypothesis, and the importance of the research.

Abuse of opioids is a significant national health problem. Pharmacogenetics, or personalized medicine, uses genotype information to predict phenotypic response (generally medication efficacy or safety). The field of substance abuse is critically lagging behind in the application of pharmacogenetics for identifying individuals at increased risk for developing an opioid abuse disorder, or using personal genetic information to guide treatment. There is growing evidence to suggest a functional polymorphism (A118G) in the OPRM1 gene that codes for the mu opioid receptor (MOR) mediates individual response to opioid medications and has direct relevance for the development of opioid dependence. To date, no controlled human laboratory studies have examined the effect of the A118G SNP or OPRM1 gene on individual response to opioids. The next logical step is to evaluate whether differences in OPRM1 single nucleotide polymorphisms (SNPs) drive individual response to opioid medications, which will help advance the field of substance abuse towards a pharmacogenetics approach to treatment, and establish a precedent for using controlled and well-validated laboratory methodology to investigate the genotype-phenotype interactions of opioids. We are proposing to conduct a laboratory study to evaluate whether the A118G SNP and additional OPRM1 tagging SNPs are associated with a variety of different MOR-mediated functions by evaluating subjective and physiological response to double-blind administration of an opioid medication. We will also evaluate the contribution of OPRM1 on other complex phenotypes related to the MOR activity or opioid dependence (e.g., pain sensitivity, the endogenous opioid-mediated cortisol stress response, and a delay discounting behavioral economic task). This study will be a between-group evaluation of genotype and sex, and a within-subject evaluation of opioid dose-response that will be conducted over 5 days in a residential clinical research unit. Study completers (n=100) will receive double-blind doses of oral hydromorphone or placebo in a randomized, counter-balanced research design. Self-report, physiological, and salivary cortisol measures of drug effects will be collected at several time points following drug administration, and delay discounting will be administered at screening and during peak drug effects. We will also administer different operant pain tasks that provide quantifiable estimates of pain sensitivity, under conditions of placebo or hydromorphone administration. This study will be the most controlled, rigorous, comprehensive examination of the A118G SNP and OPRM1 gene with opioid-mediated effects to date. We expect that genotype will be associated with several opioid-mediated effects, and that the results will advance our understanding of the contribution of OPRM1 to specific behavioral phenotypes. These data will advance the use of pharmacogenetics for substance abuse and use of laboratory testing for genotype-based hypotheses, and will contribute to the development of opioid dependence prevention strategies and interventions to treat comorbid pain and opioid dependence.

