#### 4. Study Procedures

- a. Study design, including the sequence and timing of study procedures (distinguish research procedures from those that are part of routine care).

**Study Overview:** This study will be a between-group (total completer N=100) evaluation of genotype and sex, and a within-subject evaluation of opioid dose-response. The study will be conducted over 5 days (4 nights) at the Behavioral Pharmacology Research Unit (BPRU) and a residential clinical research unit (CRU) (Figure 1). Day 1 will be an Admission day. Days 2-5 will consist of blinded study drug administration in the morning, 1 pain testing session, and self-report/physiological measures of drug effects for 6 hours post dosing. Participants will receive double-blind doses of oral hydromorphone (2mg, 4mg, 8mg) (99-102) or weight and color-matched placebo in a randomized, counter-balanced research design.

**Screening Visit:** Participants will complete a brief phone screen to determine initial eligibility and will be invited to complete an in-clinic screen. Participants will sign an informed consent form with a study staff member to begin the Screening visit. To reduce expectancy effects, the consent will inform participants the study drug may consist of one or more of numerous different drug classes (e.g., opioids, stimulants, over-the-counter medications), a common practice in laboratory based studies of drug effects (103, 104). Following consent, a staff member will administer a battery of measures to establish study eligibility (see Study Measures below). A urine sample will be collected and tested for evidence of illicit drugs and to establish medical eligibility. A blood sample of no more than 2 tablespoons will also be collected from eligible participants for medical and genotype analysis. Participants will also be asked to provide a second blood sample (2 additional tablespoons) that will be collected at either Screening or Admission and stored for future genetic analysis. This will be voluntary. Participants who meet eligibility criteria (including results of laboratory blood tests) will be scheduled for an Admission day.

**Study Day 1, Admission Visit:** Participants will complete a brief history and physical to determine final study eligibility and will be admitted to the CRU for 5 days (Admission day + 4 session days). During the Admission day, participants will be familiarized with the pain testing procedures and the measures used during session days 2-5.

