**Study Days 2-5, Session Days:** The morning of each session, participants will be provided with a standardized breakfast, and cigarette smokers will be permitted 1 cigarette the morning prior to a session (1 additional cigarette will be permitted every 2 hours during the session). Sessions may take place either at the CRU or the BPRU, however all participants will reside overnight in the CRU. Participants will receive a standardized lunch and dinner. Beginning on Day 2, participants will receive a blinded study drug in the morning, will conduct a pain testing session approximately 60-90 minutes post-dose, and will provide self-report, observer-ratings, and physiological measures of drug effects for an additional 6-hours post-dosing. Each element is described in more detail below. Participants will also provide a blood sample (no more than 1 tablespoon) that will be analyzed for metabolic status. This sample can be collected at any point during Study Days 2-5.

**Pain Testing:** Participants will undergo 1 pain-testing session each day. Sessions will consist of pressure pain threshold, conditioned pain modulation, and temporal summation testing. Participants will be oriented to the study measures and pain testing apparatuses during the Admission Day. During the sessions, study drug will be administered under double-blind conditions in the morning. Salivary cortisol samples will be collected following completion of the pain testing session to evaluate the acute stress response to each pain stimulus, as a function of

drug (placebo vs. hydromorphone). Ratings of numeric rating scales will be used for data analysis, and participants will be asked to identify whether a placebo or active drug had been administered.

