**Mechanical Temporal Summation.** Temporal summation of pain will be assessed using repetitive mechanical stimuli. The assessment of temporal summation involves rapidly applying a series of identical noxious stimuli and determining the increase in pain across trials; animal studies have suggested that temporal summation occurs centrally in second-order neurons in the spinal cord as a consequence of sustained C-fiber afferent input (149-151). For temporal summation of mechanical pain, pain ratings in response to a single punctate noxious stimulus will be compared to pain ratings in response to a sequence of identical punctate noxious stimuli (152). A weighted pinprick stimulator with a flat contact area will be used to deliver either a single pinprick stimulus or a train of 10 pinprick stimuli repeated at a constant rate. Following the single stimulus and the 10-stimulus train, the subject is asked to give a pain rating. Single pinprick stimuli are alternated with the trains of 10 stimuli. Similar procedures using this type of weighted pinprick stimulator have been used in diabetic neuropathy (153), healthy subjects (154), and to assess temporal summation (155-156).

**Acute Effects of Hydromorphone:** Participants will ingest medication under staff supervision and complete a battery of self-report, physiological, and cortisol measures will be collected prior to dosing and up to 15 time points post-dose (up to 6 hours). During the final assessment each day, participants will complete a Drug vs. Money Questionnaire modeled from the Multiple Choice Procedure to indicate the dollar value they would place upon the drug received and this measure will be repeated immediately prior to the next day's drug administration. These experimental procedures are consistent with those used in a previous study by our group (110). Participants will be discharged from the study on the final day after completing the final study assessment and a field sobriety test that indicates no persistent opioid effects. We will conduct a follow-up phone call with participants the day following discharge to document any adverse events and to administer the final Drug vs. Money Questionnaire.

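### The mid-level dose is always given at the first session, so a pooled placebo-versus-hydromorphone pain effect absorbs one third of any first-session shift

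*Combined protocol and SAP*

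**What the plan says.** Section 6.a (rationale for drug and dose) sets the order of sessions: "The first dose participants will receive is the mid-level dose, which will be administered on study Day 2". The other three conditions (placebo, low, high) follow in randomized, counter-balanced order over Days 3 to 5. The fixed first dose has a stated screening purpose. Section 6.a discharges anyone who reacts badly to it, and Table 1 in section 5 excludes participants who "Experience an adverse event that warrants opioid antagonist treatment following" the first dose.

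The summaries do not mention this exception. The Abstract describes "oral hydromorphone or placebo in a randomized, counter-balanced research design", and the Study Overview in section 4.a describes active doses "or weight and color-matched placebo in a randomized, counter-balanced research design".

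On pain testing, section 4.a says "Participants will undergo 1 pain-testing session each day", and that on session days participants "will conduct a pain testing session approximately 60-90 minutes post-dose". No pre-dose pain test is described for those days. On the Admission day, "participants will be familiarized with the pain testing procedures and the measures used during session days 2-5". For the self-report, physiological and cortisol battery, by contrast, "measures will be collected prior to dosing and up to 15 time points post-dose".

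Section 7.c (Analysis of pain testing sessions) fits random-intercept mixed models to the pressure pain threshold, the DNIC threshold and the DNIC index. The within-subject factor has two levels, placebo and hydromorphone. Age and race are the covariates. No day or session term is named, and the text does not say how the three active doses are combined or which days enter. It mentions Days 3 to 5 only for the drug effects with which the pain results will be correlated.

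**The concern.** Every participant has the mid-level dose at the first session, and nobody has placebo there. Anything particular to that session (novelty of the setting, first drug exposure, remaining unfamiliarity with the pain apparatus) therefore falls entirely on the mid-level dose. A two-level drug factor over all four sessions carries part of it into the estimated analgesic effect.

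The measures at risk are the absolute post-dose ones, namely the pressure pain threshold and the DNIC threshold. With no pre-dose test on session days, analgesia on these is a comparison between days. The DNIC index is a ratio formed within one session and is less exposed.

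At stake is the overall analgesic effect against which any lower analgesia in minor-allele carriers will be read. It could be over- or understated, since the direction of a first-session shift is unknown.

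**Working it through.** The plan states no figure for this point, so the check works from the design.

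**Inputs from the documents.** Mid-level dose on Day 2; placebo, low and high over Days 3 to 5 (section 6.a); doses 0, 2, 4 and 8 mg and 100 completers (section 4.a).

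**Assumed.** A Day 2 shift s, in units of the within-subject standard deviation of one session, taken as 0.1, 0.2 and 0.4; session errors independent given the subject intercept; equal use of the six possible orders.

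**Estimability.** With subject effects, four dose levels and four days, the design matrix has rank 11 for 12 columns, because mid-level dose and Day 2 are the same column. Low versus placebo and high versus placebo can be estimated; mid versus placebo cannot. Adding a day term to the two-level model removes the bias, but then low, mid and high receive weights 0.5, 0 and 0.5. It becomes a low/high-versus-placebo contrast.

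**Bias without a day term.**
- Low versus placebo and high versus placebo: 0.
- Mid versus placebo: s.
- Average of three active doses versus placebo: s/3.
- Linear slope on dose: mean dose 3.5 mg; Sxx = 12.25 + 2.25 + 0.25 + 20.25 = 35; bias = (4 − 3.5)s/35 = 0.0143s per mg.

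**Rejection at a nominal two-sided 5% level with no drug effect.**
- Three-dose average: variance (1 + 1/3)/100, standard error 0.1155, so z = (s/3)/0.1155 = 2.89s.
- Slope: z = 0.0143s/√(1/(35 × 100)) = 0.845s.

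| s | bias of average | average rejects | slope rejects |
|---|---|---|---|
| 0.1 | 0.033 | 6.0% | 5.1% |
| 0.2 | 0.067 | 8.9% | 5.3% |
| 0.4 | 0.133 | 21% | 6.3% |

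A simulation of 4,000 trials per value gave 6.05% at s = 0.1 and 8.98% at s = 0.2. With a true drug effect, the same s/3 is added to the estimate.

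**Genotype-by-drug contrast.** A shift common to both genotype groups cancels. If it differs between them by g, the three-dose contrast moves by g/3, with z = (g/3)/√((4/3)(1/n₁ + 1/n₂)). At g = 0.1, 0.2 and 0.4 the 5% test rejects 5.2%, 6.0% and 8.9% with a 50/50 split, and 5.2%, 5.6% and 7.5% with 20/80 (splits assumed).

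**Cost of using Days 3 to 5 only.** The variance factor for active versus placebo becomes 1 + 1/2 = 1.5 instead of 1.333; √(1.5/1.333) = 1.061, a standard error about 6% larger. If the 100 completers are spread 17/17/17/17/16/16 over six orders, the day term adds 0.01% to 0.04% to the variance. Under unrestricted randomization it adds about 1% (median of 60 simulated allocations; maximum about 4%).

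**The case against.** The strongest objection is that no stated hypothesis is touched. Sections 2 and 7 frame the directional hypotheses as genotype comparisons, and a shift shared by all genotypes cancels there. This stands. A reader might infer that the OPRM1 findings themselves are confounded; that would need a first-session effect that differs by genotype, and the documents give no evidence of one. What remains exposed is the overall drug effect.

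Second, the problem is conditional. It needs all active doses to be pooled, which section 7.c allows but does not state, and a shift that is not zero. Admission-day familiarization may have reduced the shift, by an amount not stated. This also stands: every value of s and g above is an assumption. The reference to Days 3 to 5 in section 7.c may suggest that the authors set Day 2 apart, but it governs only the correlation with drug effects, not the pain model.

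Third, the fixed first dose is deliberate and openly described, and the summaries are overview sentences. That answers any suggestion that the order is a mistake. It does not make the mid-level dose separable from the first session.

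Fourth, dropping Day 2 everywhere would lose the only intermediate active dose in a dose-response design, for a slope that is nearly unaffected. This is correct, and it is why the restriction should not reach the dose-response models in the Association Model paragraph.

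**Conclusion.** The concern holds in a limited form. The mid-level dose is fully aliased with the first session. If the two-level drug term uses all sessions, the drug main effect on the pressure pain threshold and the DNIC threshold takes up one third of any Day 2 shift, with unknown sign. For an assumed shift of 0.1 to 0.4 within-subject standard deviations, the bias is 0.033 to 0.133 of that unit.

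The documents do not support the broader reading that all dose comparisons are compromised: low and high versus placebo rest on randomized sessions. Priority is minor to moderate, because the remedy is cheap and settles in advance which sessions define analgesia.

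**What to change.** Leave dosing unchanged and amend the text.

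1. In section 7.c, Analysis of pain testing sessions, estimate the active-versus-placebo main effect from the randomized Days 3 to 5, with study day as a fixed effect, and label it a low/high-versus-placebo contrast. A day term cannot recover the mid-level contrast. Cost: a standard error about 6% larger, and no contribution from the mid-level dose to this estimate.
2. Keep all doses in the primary genotype-by-drug and dose-response analyses, label Day 2 as a non-randomized first-exposure session, and add a sensitivity analysis on Days 3 to 5 only. The main effect and the genotype test can then be read on the same dose mix. The primary tests lose nothing; the sensitivity version of the genotype-by-drug test has a standard error about 6% larger.
3. Reconcile the design wording in the Abstract and the Study Overview with section 6.a by stating that randomization and counter-balancing apply to Days 3 to 5.

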**Association Model:** Our primary goal is to demonstrate the impact of SNP variation across OPRM1 on variability in response to hydromorphone across time and dose. Association analyses will be performed by modeling genotype at each SNP in a general linear model. In its simplest form this test, commonly termed the measured genotype analysis (137), models the influence of genotypic variation at a given locus on variation in the quantitative trait, essentially a one-way Analysis of Variance (ANOVA). This approach provides a distinct advantage in that it can easily be extended to a two-way ANOVA to model genotype effects across 3 different doses of drug. In addition, the flexibility of the GLM allows incorporation of ancestry covariates and environmental moderators or mediators. We will examine the impact of OPRM1 at each time-point in separate analyses and account for the multiple testing using LD-adjusted Bonferroni correction (see below).

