**Analysis of pain testing sessions:** We hypothesize that OPRM1 SNP variants will exhibit greater pressure pain thresholds, greater CPM efficiency, lower hydromorphone-related analgesia, and lower cortisol stress response than participants with the major allele, and that results will be positively correlated with response to self-report and physiologically-mediated hydromorphone drug effects collected during days 3-5. Pressure pain threshold will be estimated by averaging the results of the 2 administrations to radiobrachialis and quadriceps muscle groups. We will generate a CPM index for each participant [(mean pressure pain threshold during cold pressor)/(mean pressure pain threshold prior to cold pressor)] x 100 (90). These values will provide a quantitative measure of percent change in the test stimulus (i.e., pressure point threshold). Mixed effects regression models with a random intercept will be used to compare dependent variables (pressure pain threshold, DNIC threshold, DNIC index) as a function of within-subject drug effects (placebo vs. hydromorphone), and between-subject effects of OPRM1 SNP analysis will be conducted as specified in Aim 1. Gender, age, and race have been associated with response to pain and the CPM test (146-148). Gender will be evaluated using independent subgroup analyses and age and race will be included as covariates. Finally, subscale scores of self-report measures of pain and coping strategies will be compared between the two genotype groups using independent samples t-tests, and drug identification data will be compared using a chi-square for each drug condition. We expect that both experimental manipulations will induce pain in the minor and major allele groups, and that participants with the minor allele will demonstrate lower sensitivity to pain (e.g., greater pressure pain magnitudes), lower NRS ratings of pain, lower cortisol response to painful stimuli, and lower analgesic relief from hydromorphone compared to the major allele participants.

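### Neither stated model contains session day, although dose order is counter-balanced over Days 3-5: a small, avoidable loss of precision, mainly in genotype-by-drug contrasts

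*Combined protocol and SAP*

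**What the plan says.** Section 6a sets the order of the sessions. On Day 2, "The first dose participants will receive is the mid-level dose, which will be administered on study Day 2". Placebo and the low and high doses follow on Days 3-5, and "the order of doses will be randomized and counter-balanced". The overview in section 4a describes the whole scheme as "weight and color-matched placebo in a randomized, counter-balanced research design", without mentioning the fixed Day 2 dose.

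Section 7c describes two models.

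- **Association Model.** A genotype ANOVA is preferred because "it can easily be extended to a two-way ANOVA to model genotype effects across 3 different doses of drug". On covariates it says that "the flexibility of the GLM allows incorporation of ancestry covariates and environmental moderators or mediators". On time it says: "We will examine the impact of OPRM1 at each time-point in separate analyses". No participant term is mentioned.
- **Analysis of pain testing sessions.** This is a mixed model with a random intercept. Pain outcomes are compared "as a function of within-subject drug effects (placebo vs. hydromorphone", so drug is described with two levels, alongside OPRM1 genotype. Age and race are covariates, and sex is handled by subgroup analysis.

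No session-day, period, order or sequence term appears in either model or elsewhere in section 7. The separate time-points are most naturally the repeated post-dose assessments of section 4a. If they did mean days, separate analyses by day would still not adjust a within-person contrast.

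**The concern.** When treatment order is balanced over days, the usual crossover analysis includes the day. Balancing keeps drift from biasing the condition contrasts on average. Only a day term also takes the drift out of the residual.

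Drift is plausible here. The same pain tests and the delay-discounting task are repeated on every session day, and participants live in the unit for five days.

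The contrasts at stake are drug versus placebo within person, and the difference in that contrast between genotype groups. The second matters more: lower analgesic efficacy in minor-allele carriers is a hypothesis about a primary outcome in section 7a, and it is a genotype-by-drug contrast. Nothing in the documents says that order is balanced within genotype. A small carrier group could by chance receive placebo earlier or later than non-carriers, and drift would then add noise to the estimate itself.

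**Working it through.** **Inputs.** From the documents: three conditions over Days 3, 4 and 5 (section 6a), 100 completers (section 4a), and a test level of .001 (section 7c). Assumed, because the documents are silent: linear drift δ of 0.1-0.3 total SD per day, and a within-person correlation r of .5-.7. The plan gives no figure for drift or for the precision of a drug contrast. Its power statement concerns a mean difference between genotype groups, so it is not a benchmark for this point.

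**1. Day difference between two conditions.** Over the six possible orders, the day of the high dose minus the day of placebo is ±1 with probability 2/3 and ±2 with probability 1/3. Its mean is 0, so there is no bias. Its variance is (2/3)(1) + (1/3)(4) = 2. A three-order Latin square gives differences 2, -1 and -1, again with mean 0 and variance (4 + 1 + 1)/3 = 2. The result does not depend on which scheme is used.

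**2. Contrast variance.** With total SD 1, the within-person residual variance is s² = 1 - r. Without a day term, high minus placebo has variance 2(1 - r) + 2δ². The day term removes 2δ². The inflation factor is therefore 1 + δ²/(1 - r).

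| δ per day | r | Variance | Interval width (square root) |
|---|---|---|---|
| 0.1 | .5 | 1 + 0.01/0.5 = 1.02 | 1.01 |
| 0.1 | .7 | 1 + 0.01/0.3 = 1.03 | 1.02 |
| 0.2 | .5 | 1 + 0.04/0.5 = 1.08 | 1.04 |
| 0.2 | .7 | 1 + 0.04/0.3 = 1.13 | 1.06 |
| 0.3 | .5 | 1 + 0.09/0.5 = 1.18 | 1.09 |
| 0.3 | .7 | 1 + 0.09/0.3 = 1.30 | 1.14 |

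The average of low and high minus placebo gives the same factor: its day difference has variance 1.5 and its residual variance is 1.5s².

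**3. Simulation of the genotype-by-drug contrast.** Assumptions: 102 participants for exact balance, 20 of them carriers, person-centred regression, 4,000 runs. The variance ratio without versus with the day term was 1.00-1.02 at 0.1 SD per day, 1.07-1.12 at 0.2 and 1.19-1.32 at 0.3. A second simulation used equal genotype groups and drift of half a within-person SD per day. The standard errors were 0.315 without and 0.281 with the day term, a variance ratio of (0.315/0.281)² = 1.26, against 1 + 0.5² = 1.25 from the formula.

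**4. In terms of power.** Take a contrast that has 80% power at .001 once drift is removed. It would have about 70% with 18% inflation and about 63% with 30%.

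**5. What the day term cannot reach.** The mid-level dose is always on Day 2, while placebo falls on Day 4 on average. The expected day difference is 2 - 4 = -2. For all three active doses pooled it is (2 + 4 + 4)/3 - 4 = -0.67. Drift therefore shifts these two drug contrasts by -2δ and -0.67δ. Day and dose coincide there, so no day factor can separate them.

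**The case against.** **The size is assumed.** The documents neither report nor predict drift, and at 0.1 SD per day the loss is trivial. The 30% figure needs 0.3/√0.3 = 0.55 within-person SD per day, or 1.1 between Day 3 and Day 5. Participants are familiarised with the tests at admission and complete a full session on Day 2, so some practice and habituation should precede the randomised days. This stands, and the low end of the range is quite possible.

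**Many results are barely touched.** Pupil and blood-pressure outcomes are changes, and conditioned pain modulation is scored against a same-session baseline, so additive drift in level largely cancels. Every completer passes through the same days, so the genotype effect averaged over sessions hardly moves. This also stands. The point fits outcomes analysed as raw levels best, such as pressure pain threshold.

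**The arithmetic presupposes a participant term.** The Association Model as written has none. Its error is then the total variance, to which drift adds only (2/3)δ², or 0.7-6%. A day term alone would not deliver the tabulated gain there. This stands and shapes the fix.

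**Stronger readings to avoid.** A reader might infer that the omission biases the drug effect. Over Days 3-5 it does not: the mean day difference is 0, and with exact counter-balancing the drug main-effect estimate is unchanged and only its model standard error is too large. A reader might infer that order is unbalanced by genotype. The documents are silent, so imbalance is a matter of chance, not a stated feature. Nor is the counter-balancing wasted, since it already protects against bias on average.

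**Conclusion.** The omission is confirmed in both models. Its consequence is confined to precision for the placebo, low and high conditions. Drug contrasts get standard errors that are too large, and genotype-by-drug contrasts lose real precision as well. On the stated assumptions the cost is 2-30% in variance, or about 1-14% in interval width. It depends on an unknown drift and on drift being common to all participants. It is a minor point, worth taking because the remedy is nearly free and is better fixed in advance than chosen after the data are seen.

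It does not call the main genotype comparison into question, and a day term would not repair the Day 2 confounding, which is a separate matter.

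**What to change.** In section 7c:

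1. Add session day (3, 4, 5) as a categorical fixed effect for the randomised placebo, low and high sessions to the pain mixed model. Do the same in the Association Model once it is fitted with a participant term.
2. Enter condition as a four-level factor (placebo, low, mid, high), with its interaction with genotype where that is the question, so that Day 2 data can stay in the model. Take the day-adjusted drug contrasts from placebo, low and high.
3. State that the mid-level coefficient is aliased with Day 2, that the day term does not correct it, and that any pooled active-versus-placebo contrast including it inherits the same limitation.

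The cost is a few lines of analysis wording and two degrees of freedom out of about 200 within person (100 × 3 sessions - 100 participants). No procedure, dose or sample size changes.
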